4.3 Patients' satisfaction for medical treatment (TSQM-9) (primary objective)

Table 10. Patients' satisfaction for medical treatment (TSQM-9 items) at each study visit

The table will provide absolute and relative frequency of patients' answers to TSQM-9 items (see Appendix 8.3) at each study visit.

Percentages will be calculated over the number of patients respectively evaluable at the time point considered, namely at enrollment (i.e. FAS patients), at 6 months (i.e. evaluable patients at 6 months) and at 12 months (i.e. evaluable patients at 12 months).

Table 11. Patients' satisfaction for medical treatment (TSQM-9 subscales) at each study visit

The table will provide the descriptive statistics (mean, median, standard deviation, quartiles, min, max) of the TSQM-9 subscales scores (as defined in "Computed variables" chapter) at each study visit.

Changes from enrollment in TSQM-9 subscales scores (see 'Computed variables' chapter) will be also summarized by visit.

95% confidence intervals limits of the mean will be provided for each estimate (i.e. TSQM-9 subscales scores and changes). Descriptives will be calculated over the number of patients respectively evaluable at the time point considered, namely at enrollment (i.e. FAS patients), at 6 months (i.e. evaluable patients at 6 months) and at 12 months (i.e. evaluable patients at 12 months).

4.4 Patients' disease perception (B-IPQ) (secondary objective #1)

Table 12. Patients' disease perception (B-IPQ) at each study visit

The table will provide the descriptive statistics (mean, median, standard deviation, quartiles, min, max) of B-IPQ questionnaire total score (as defined in "Computed variables" chapter) at each study visit.

Changes from enrollment in B-IPQ total score (see 'Computed variables' chapter) will be also summarized by visit.

95% confidence intervals limits of the mean will be provided for each estimate.

Descriptives will be calculated over the number of patients respectively evaluable at the time point considered, namely at enrollment (i.e. FAS patients), at 6 months (i.e. evaluable patients at 6 months) and at 12 months (i.e. evaluable patients at 12 months).

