(Brief IPQ) that is a validated 9-item questionnaire designed to rapidly assess cognitive and emotional representations of illness (ref Broadbent 2006). All of the questionnaire items (except the causal question, item 9) are rated using a 0-to-10 response scale (17). Five of the items assess cognitive illness representations: consequences (Item 1), timeline (Item 2), personal control (Item 3), treatment control (Item 4), and identity (Item 5). Two of the items assess emotional representations: concern (Item 6) and emotions (Item 8). One item assesses illness comprehensibility (Item 7). Assessment of the causal representation is by an opened response item, which asks patients to list the three most important causal factors in their illness (Item 9).

The questionnaire will be completed by patients at enrolment, 6- and 12-month follow up visits.

Morisky medication Adherence Scale 4 items (MMAS-4)

The MMAS-4 is a self-reported, medication-taking behavior scale and consists of four questions about the way patients might experience drug errors or omissions. Each item has a scoring scheme of “Yes” = 0 and “No” = 1. Items are summed to give a non-adherence score ranging from 0 to 4 (42-44); higher score means better adherence to therapy.

The scale will be completed by patients at enrolment, 6- and 12-month follow up visits.

COPD Assessment Test (CAT)

During the 12-month observation period the COPD symptoms will be evaluated by the COPD Assessment Test (CAT). The CAT is an 8-item unidimensional measure of health status impairment in COPD (41). It is designed to measure the impact of COPD on a person's life, and how this changes over time. It contains eight short, simple, patient-completed questions. Patients can choose a score from 0 to 5 for the extent to which the described impairment is true for them, thereby providing a measure of the impact of COPD on their individual health.

The score ranges from 0 to 40; higher scores represent worse health. The CAT score is calculated as the sum of the responded items.

The questionnaire will be completed by patients at enrolment, 6- and 12-month follow up visits.

Modified Medical Research Council (MMRC) dyspnea scale

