The patients switching treatment during observation period will not be excluded from analysis and will be evaluated at each visit as above described. Few patients are expected to stop treatment during study; if any, for primary objective evaluation they will be censored at the latest available visit. Comparisons of satisfaction between different treatment/devices are not matter of this study, throughout all analysis treatments will be lumped together.

Secondary objectives

#1 To describe patient disease perception (B-IPQ), adherence to COPD treatment (MMAS4), health status (CAT) and dyspnea (MMRC) during a 12-month observation period

A description of B-IPQ (consequences, timeline, personal control, treatment control, identity, concern, emotions and illness comprehensibility), MMAS-4, CAT and MMRC scores will be provided at baseline and at follow-up visits. Scale scores will be summarized at each time point. Patients lost to follow up will be considered until their last available visit. Missing items of questionnaires/scales will be replaced if applicable according to scoring algorithm [32-38].

#2 To analyse the relation between treatment satisfaction for medical treatment and demographic/clinical parameters and PROs during a 12-month observation period

Three regression models (one for each TSQM-9 domain score) will be estimated; the dependent variable will be domain score and the independent ones will be: age and gender (at enrollment), number of exacerbations, relevant spirometry parameters (such as FEV1, FVC, FEV1 % of the predicted, RV, TLC, DLCO), level of dyspnea (MMRC score), impact of COPD on a patient's life (CAT) and treatment adherence (MMAS-4 score) collected during observational period. Because dependent variable will be collected at each study visit, repeated measures models will be estimated taking into account all available values for dependent and independent variables. Patients could be classified in mild or moderate/severe according to lung function parameters. This will allow to evaluate treatment satisfaction in different groups of patients.

The patients switching treatment during observation period will not be excluded from analysis and will be evaluated at each visit. The patients stopping treatment during study will be censored at last available visit.

#3 To describe the health care resources utilization and related cost during a 12-month observation period

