1 STATISTICAL ANALYSIS PLAN OBJECTIVES

The *SATisfaction and adherence to COPD treatment* study (i.e. SAT study) is a multi-center, non-interventional (observational) cohort study based mainly on newly collected data. About 400 consecutive COPD patients will be enrolled in approximately 8 months (from first patient enrolled). Patients will be followed up for 1 year, with an intermediate evaluation after 6 (+/-1) months from baseline (which is compatible with current clinical practice in Italy for COPD patients management).

The present Statistical Analysis Plan has been designed considering the following input documents:

- the Study Protocol v.1.0 31/07/2015,
- the electronic case report form v. 1.2 27/04/2016;
- the minutes of the Customer's Meeting held on the 26/06/2017.

This SAP is aimed at evaluating the following SAT study objectives:

Primary objective:

To describe the patients' satisfaction to COPD medical treatments (by means of the TSQM9) during a 12-month observation period (namely, at enrolment, and after 6 and 12 months) in real- world setting.

Secondary objectives:

1. To describe patient disease perception (by means of illness perception questionnaire B-IPQ), adherence to COPD treatment (by means of MMAS4), health status (by means of CAT questionnaire) and dyspnea (by means of mMRC) during a 12-month observation period.
2. To analyze the relation between treatment satisfaction and demographic (such as age, gender), clinical (such as number of exacerbations, spirometric parameters) parameters and PROs during a 12-month observation period.
3. To describe the health care resources utilization and related cost according to the Italian National Health Service (INHS) during a 12-month observation period.
4. To assess the correlation between patients' satisfaction and resource utilization.

In this document the eCRF fields are indicated as follows: "label of the field" [*name of the eCRF form.name of the variable in the dataset*].

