The B-IPQ total score will be computed as follows: the reversed scores of items 3, 4, and 7 [F14_BIPQ.BIPQ_3, BIPQ_4, BIPQ_7] will be added to the scores of items 1, 2, 5, 6, and 8 [F14_BIPQ.BIPQ_1, BIPQ_2, BIPQ_5, BIPQ_6, BIPQ_8]. A higher score reflects a more threatening view of the illness). The B-IPQ total score can be computed only if items #1-8 are filled in: only item 9 can be missing. Missing values will not be replaced.

Changes in the B-IPQ total score at each follow-up visit from enrollment will be calculated, for each patient, as the following difference: (score at 6/12 months - score at enrollment), if both scores are available.

TSQM-9 subscales scores

The Treatment Satisfaction Questionnaire for Medication, 9 items (TSQM-9) was derived from the original version, and it has a total of 9 items with responses to nearly all items rated on a five-point or seven-point rating scale that provide scores on three scales: effectiveness (3 items), convenience (3 items) and global satisfaction (3 items). The TSQM-9 domain scores (effectiveness, convenience and global satisfaction) will be calculated as recommended by the instrument authors (Atkinson MJ, Kumar R, Cappelleri JC, Hass SL: Hierarchical construct validity of the treatment satisfaction questionnaire for medication (TSQM version II) among outpatient pharmacy consumers. *Value Health*. 2005 Nov-Dec;8 Suppl 1:S9-S24).

In particular, Here below is provided the algorithm to compute each domain score:

- Effectiveness = [(item1 + item2 + item3) - 3]/18*100 = [(TSQM9_1+TSQM9_2+TSQM9_3) - 3]/18*100
- Convenience = [(item4 + item5 + item6) - 3]/18*100 = [(TSQM9_4+TSQM9_5+TSQM9_6) - 3]/18*100
- Global satisfaction = [(item7 + item8 + item9) - 3]/14*100 = [(TSQM9_7+TSQM9_8+TSQM9_9) - 3]/14*100

Each domain score can be calculated only if all the three items considered in the calculation of that score are not missing. Missing values will not be replaced.

The TSQM-9 domain scores range from 0 to 100 with higher scores representing higher satisfaction on that domain.

Changes in the TSQM-9 subscale scores at each follow-up visit from enrollment will be calculated, for each patient, as the following difference: (subscales score at 6/12 months - subscale score at enrollment), if both scores are available.

MMAS-4 score

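### SAP Table 12 reports only a B-IPQ total, whereas Protocol 9.7 names eight B-IPQ dimensions to be described; the narrowing is not declared

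*SAP*

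**What the plan says.** For the enrolment visit and both later visits, Protocol 9.7 (secondary objective #1) states: "A description of B-IPQ (consequences, timeline, personal control, treatment control, identity, concern, emotions and illness comprehensibility), MMAS-4, CAT and MMRC scores will be provided". The paragraph then adds this on timing: "Scale scores will be summarized at each time point". Protocol 9.3 assigns each of the eight dimensions to one item rated 0 to 10. Item 9 is an open question on causes. The protocol defines no B-IPQ total.

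SAP 1 repeats the objective without narrowing it, and SAP 3 repeats the assignment of items to dimensions. SAP 3 then defines one score, the sum of items 1, 2, 5, 6 and 8 and the reversed items 3, 4 and 7, with this condition: "The B-IPQ total score can be computed only if items #1-8 are filled in: only item 9 can be missing". No replacement of blank answers is allowed.

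For every visit, with 95% confidence limits, SAP 4.4 (Table 12) specifies: "The table will provide the descriptive statistics (mean, median, standard deviation, quartiles, min, max) of B-IPQ questionnaire total score". On change it says: "Changes from enrollment in B-IPQ total score (see 'Computed variables' chapter) will be also summarized by visit". It mentions no item or dimension.

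**The concern.** The eight dimensions are the only B-IPQ quantities that the protocol's analysis section names, and the SAP text provides for none of them. Table 12 is also the only planned B-IPQ output. The questionnaire is not a covariate in the objective #2 models (SAP 4.9) and is not in the objective #4 correlations (SAP 4.11). What Table 12 omits is therefore reported nowhere else in the listed tables.

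Two things are at stake. First, a total does not show which beliefs moved, although Protocol 7 presents illness and medication beliefs as determinants of adherence. Second, the completeness rule sets aside answers to seven items whenever the eighth is blank.

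**Working it through.** The plan gives no figure to reproduce on this point. The check is a comparison of texts, followed by an illustration.

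**Comparison**

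- Promised in Protocol 9.7: eight named dimensions at baseline and follow-up. Specified in SAP 4.4: no dimension summaries and one total.
- Other places in the SAP: in the list of section 5 tables, B-IPQ appears only in Table 12. The quality check for that table in SAP 6 refers only to the total.
- Declared departures: SAP 4.9 states and dates a departure from Protocol 9.7 for the objective #2 covariates. There is no such statement for B-IPQ. No entry in SAP 7 names B-IPQ, although several entries record only a general review.
- Other instruments: item-level output is planned for TSQM-9 (Table 10), MMAS-4 (Table 13) and the awareness interview (Table 16), but not for CAT (Table 14). The protocol describes CAT as unidimensional and names no CAT dimensions.

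**Netting in the total**

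Item 4 (treatment control) enters reversed and item 6 (concern) enters as answered. If both rise by 2 points, the total changes by −2 + 2 = 0.

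The SAP's own appendices give a second example. An item 2 answer nearer to lifelong illness raises the B-IPQ total, which is read as more threat. In Appendix 8.1, agreeing that one's COPD will never heal (awareness item 19) scores as better knowledge. A patient who becomes better informed can therefore look worse on the total.

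**Completeness rule**

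Inputs: eight required items (SAP 3), and 320 to 380 evaluable patients (Protocol 9.5). The per-item missing rate m is assumed, because the documents give none. With independence across items:

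- share of forms with a computable total = (1 − m)^8
- share of forms that lose the total = 1 − (1 − m)^8
- share of change scores lost, with independence across the two visits as well = 1 − (1 − m)^16

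| m (assumed) | (1 − m)^8 | Total lost | Totals from 380 / 320 forms | Answers to one item from 380 / 320 forms | Change lost |
|---|---|---|---|---|---|
| 0.5% | 0.961 | 3.9% | 365 / 307 | 378 / 318 | 7.7% |
| 1% | 0.923 | 7.7% | 351 / 295 | 376 / 317 | 14.9% |
| 2% | 0.851 | 14.9% | 323 / 272 | 372 / 314 | 27.6% |
| 5% | 0.663 | 33.7% | 252 / 212 | 361 / 304 | 56.0% |

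For a given m, the loss of totals can be as low as m, when the same forms lack every item, and cannot exceed 8m. Independence lies towards the upper end: at m = 2% it gives 14.9%, within a range of 2% to 16%. Clustering within patients would reduce the loss.

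**The case against.** The strongest case on the other side has four parts.

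- **The objective itself does not mention dimensions.** Protocol 8 and SAP 1 ask only that disease perception be described by means of the B-IPQ, and the protocol abstract speaks only of B-IPQ scores. The list in 9.7 is a parenthesis that could describe the questionnaire's content. This stands in part. A reader might infer that objective #1 goes undelivered, and the documents do not support that: a total with changes by visit can satisfy the objective's wording, and Tables 13 to 15 cover MMAS-4, CAT and mMRC. The shortfall is against the fuller description in 9.7, where the eight dimensions are the only B-IPQ scores named.
- **The table shells cannot be seen.** The section 5 layouts are absent from the text available, so item rows in the Table 12 layout cannot be excluded. This stands as a limit. The written specification and the table title give no sign of such rows, whereas Table 10 is labelled as an item table.
- **Little is lost when an item is blank.** A reader might infer that one blank item removes the patient. It does not. FAS entry depends on TSQM-9 (SAP 2.1), and the footnote to Chart 1 admits patients score by score and visit by visit. Only that visit's total and any change score that uses it are lost. The TSQM-9 domains also require all their items. Data review and monitoring should help keep missing answers low.
- **Any composite nets its parts.** That is true, and the reversals make all eight items point the same way. It is no reason to leave out components that the protocol names.

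**Conclusion.** The point holds as an undeclared narrowing between Protocol 9.7 and SAP 4.4, confined to the B-IPQ part of secondary objective #1. Eight dimensions are named in the protocol, and the SAP text specifies one total in their place. This rests on the written specification and the list of tables, not on the layouts.

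The output is descriptive and no hypothesis test depends on it, so the consequence is a less informative answer on disease perception, not a biased primary result. The loss of totals, about 4% to 34% of forms for assumed item-missing rates of 0.5% to 5%, is an illustration and not a forecast. The mismatch between the documents does not depend on it.

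**What to change.** Add eight rows to Table 12, one for each of B-IPQ items 1 to 8, with descriptive statistics at each visit. Each row should use its own non-missing denominator and show that number. Report the items as answered, and note that items 3, 4 and 7 are reversed in the total. Change from enrolment and 95% confidence limits for each item are optional; they would match what is given for the total, but the protocol does not ask for them by dimension. Keep the total and its completeness rule as an additional row.

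The cost is eight more rows in one table, from data already collected. If the sponsor prefers to report the total alone, the SAP should state this as a departure from Protocol 9.7 and give the reason, as SAP 4.9 states its own departure. That would settle the inconsistency but would not restore the dimension summaries.

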4.5 Patients' adherence to COPD treatment (MMAS-4) (secondary objective #1)

Table 13. Patients' adherence to COPD treatment (MMAS-4) at each study visit

The table will provide patient distribution by MMAS-4 answers to items #1-4 (Yes/No) at each study visit.

95% confidence intervals limits will be provided for each proportion. Moreover descriptive statistics (mean, median, standard deviation, quartiles, min, max) of MMAS-4 questionnaire total score (as defined in "Computed variables" chapter) at each study visit.

Changes from enrollment in MMAS-4 total score (see 'Computed variables' chapter) will be also summarized by visit.

Descriptives will be calculated over the number of patients respectively evaluable at the time point considered, namely at enrollment (i.e. FAS patients), at 6 months (i.e. evaluable patients at 6 months) and at 12 months (i.e. evaluable patients at 12 months).

(Missing values will be replaced according scoring algorithm as defined in "Computed variables" chapter, maximum one missing value is accepted).

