9. RESEARCH METHODS

9.1 STUDY DESIGN

This is a multi-center, non-interventional (observational) cohort study based mainly on newly collected data.

In 20 Italian Pulmonary Centres about 400 consecutive COPD patients will be enrolled in approximately 8 months (from first patient enrolled). Patients will be followed up for 1 year, with an intermediate evaluation after 6 (+/-1) months from baseline (which is compatible with current clinical practice in Italy for COPD patients management).

No treatment will be administered to the patients on the protocol basis, since this is a non-interventional study and the assessment and treatment of the enrolled patients will be applied according to standard clinical practice. The patients switching or stopping treatment during observation period will not be withdrawn from the study. Few patients are expected to stop treatment during study; if any, for primary objective evaluation they will be censored at the latest available visit.

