2.2 Patients evaluable at 6-month follow-up

All enrolled patients meeting the following criteria will be considered evaluable at enrollment and at 6 month follow-up visit:

Patients considered evaluable at enrollment (i.e., responding to criteria of par 2.1 Full Analysis Set) who fulfill also the following criteria (i.e. all FAS patients who performed the 6-month follow-up visit and with at least one Treatment Satisfaction Questionnaire for Medication (TSQM-9) domain score calculated at the 6-month follow-up visit).

Criterion 11: Data collected at 6-month follow-up

- "Data collected at 6 (\pm 1) month follow up?" = "Yes" [F19_PATIENT_DISPOSITION, 6 month f-up.PD_1]

Criterion 12: Follow-up performed 6+/- 1 month from enrollment

- (Date of follow up visit (dd/mmm/yyyy) [F19_PATIENT_DISPOSITION, 6 month f-up.PD_2] – Date of enrolment visit (dd/mm/yyyy) [_PatientInfo. Date_enrollment]/30.4375 \geq 5) AND
- (Date of follow up visit (dd/mmm/yyyy) [F19_PATIENT_DISPOSITION, 6 month f-up.PD_2] – Date of enrolment visit (dd/mm/yyyy) [_PatientInfo. Date_enrollment] /30.4375 \leq 7)

The Biostatistician will evaluate the opportunity to apply a tolerance window during the analysis of data; the Sponsor will be informed of any possible changes in this range.

Criterion 13: patients with at least one Treatment Satisfaction Questionnaire for Medication (TSQM-9) domain score calculated at 6-month follow-up visit

- TSQM-9 items #1,2,3 [TSQM9_1-3] not missing & \neq "Non risponde" at 6-month follow-up, OR
- TSQM-9 items #4,5,6 [TSQM9_4-6] not missing & \neq "Non risponde" at 6-month follow-up, OR
- TSQM-9 items #7,8,9 [TSQM9_7-9] not missing & \neq "Non risponde" at 6-month follow-up

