2.3 Patients evaluable at 12-month follow-up

All enrolled patients meeting the following criteria will be considered evaluable at enrollment and at 12 month follow-up visit:

Patients considered evaluable at enrollment (i.e., responding to criteria of par 2.1 Full Analysis Set) who fulfill also the following criteria (i.e. all FAS patients who performed the 12-month follow-up visit and with at least one Treatment Satisfaction Questionnaire for Medication (TSQM-9) domain score calculated at the 12-month follow-up visit).

Criterion 14: Data collected at 12-month follow-up

- "Data collected at 12 (\pm 1) month follow up?" = "Yes" [F19_PATIENT_DISPOSITION, 12 month f-up.PD_1]

Criterion 15: Follow-up performed 12+/- 1 month from enrollment

- (Date of follow up visit (dd/mmm/yyyy) [F19_PATIENT_DISPOSITION, 12 month f-up.PD_2] – Date of enrolment visit (dd/mm/yyyy) [_PatientInfo. Date_enrollment]/30.4375 \geq 11) AND
- (Date of follow up visit (dd/mmm/yyyy) [F19_PATIENT_DISPOSITION, 12 month f-up.PD_2] – Date of enrolment visit (dd/mm/yyyy) [_PatientInfo. Date_enrollment] /30.4375 \leq 13)

The Biostatistician will evaluate the opportunity to apply a tolerance window during the analysis of data; the Sponsor will be informed of any possible changes in this range.

Criterion 16: patients with at least one Treatment Satisfaction Questionnaire for Medication (TSQM-9) domain score calculated at 12-month follow-up visit

- TSQM-9 items #1,2,3 [TSQM9_1-3] not missing & \neq "Non risponde" at 12-month follow-up, OR
- TSQM-9 items #4,5,6 [TSQM9_4-6] not missing & \neq "Non risponde" at 12-month follow-up, OR
- TSQM-9 items #7,8,9 [TSQM9_7-9] not missing & \neq "Non risponde" at 12-month follow-up

Three sets of patients have been identified for the evaluation of SAT study objectives. Chart 1 displays the analysis sets considered for the statistical analyses foreseen in the Study Protocol.

Chart 1: Sets of patients considered for each statistical analysis

| | Patients evaluable at enrollment (FAS) | Patients evaluable at enrollment and at 6 month follow-up | Patients evaluable at enrollment and at 12 month follow-up |
|--|---|--|---|
| Enrolled and evaluable patients | X | X | X |
| Main socio-demographics and life habits (age, gender, race, education, employment status) at enrollment | X | | |
| Medical history for COPD (number of exacerbations in the 12 months prior to enrollment) | X | | |

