| Patients' satisfaction to COPD medical treatments (by means of the TSQM9) at each study visit | X* | X* | X* |
| Patient disease perception (by means of illness perception questionnaire B-IPQ) at each study visit | X* | X* | X* |
| Patient adherence to COPD treatment (by means of MMAS4) at each study visit | X* | X* | X* |
| Patient health status (by means of CAT questionnaire) at each study visit | X* | X* | X* |
| Measurement of dyspnea (by means of mMRC) at each study visit | X* | X* | X* |
| Patient's COPD awareness (COPD awareness questionnaire) at each study visit | X* | X* | X* |
| Relation between treatment satisfaction and demographic (such as age, gender), clinical (such as number of exacerbations, spirometric parameters) parameters and PROs during a 12-month observation period | | | X |
| Description of health care resources utilization and related cost according to the Italian National Health Service (INHS) during a 12-month observation period. | X | | |
| To assess the correlation between patients' satisfaction and resource utilization during a 12-month observation period | | | X |
| Ongoing pharmacological and non-pharmacological treatments for COPD | X | | |
| Exacerbations occurred during observation period | X | | |

*Patients having PRO score computable at the visit will be considered for this analysis (i.e. PRO filled in at the visit and having a sufficient number of items recorded to allow score computation (PROs computation details are reported in Section 3. "Computed Variables"))).

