The Morisky medication Adherence Scale 4 items (MMAS-4) is a self-reported, medication-taking behavior scale and consists of four questions about the way patients might experience drug errors or omissions. Each item [F13_MMAS_4.MMAS_4_1 - MMAS_4_4] has a scoring scheme of "Yes" = 0 and "No" = 1. Items are summed to give a non-adherence score ranging from 0 to 4; a higher score means better adherence to therapy (Morisky DE, Green LW, Levine DM. Concurrent and predictive validity of a self-reported measure of medication adherence. *Med Care*. 1986 Jan;24(1):67-74).

The score can be calculated if at least 3 out of 4 of the items are completed. If only one item is omitted, the value for the missing item is the group median of this item that has been completed by all eligible participants. This median value will be imputed for all eligible cases who did not answer this item.

Changes in the MMAS-4 score at each follow-up visit from enrollment will be calculated, for each patient, as the following difference: (score at 6/12 months - score at enrollment), if both scores are available.

COPD pharmacological treatments (classes) ongoing at enrollment

All COPD pharmacological treatments having "End date of therapy" [F20_COPD_PHARMACOLOGICAL_THERAPY.END_DATE_THER] > "Date of enrollment visit" [PatientInfo.Date_enrollment] OR ("End date of therapy" missing and "Ongoing at the end of observation?" [F20_COPD_PHARMACOLOGICAL_THERAPY.ONGOING_THER] = "Yes").

Drug names will be coded by CDM and grouped according to the following categories:

- LAMA alone
- LABA alone

- ICS alone
- LABA + LAMA (Fixed dose combination or not)
- LABA + ICS (Fixed dose combination or not)
- LABA + LAMA + ICS
- SABA or SAMA on demand
- Other: pharmacological therapies for COPD not included in the previous classes.

Categories above are not mutually exclusive: a patient could be classified in more than one category (i.e. if a patient is receiving LABA and SABA on demand, [REDACTED] will be classified both in the “LABA alone” and in the “SABA or SAMA on demand” classes). Only therapies for COPD will be considered (i.e. those records with field Therapy for [F20_COPD PHARMACOLOGICAL THERAPY.THERAPY_FOR] = “COPD”), while therapies for COPD exacerbations or for COPD-related adverse events will not be considered nor classified.

COPD pharmacological treatments (classes) ongoing at 6- and 12-month follow-up visit

At each follow-up visit, all COPD treatments classes (see algorithm above) having

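### At 6 and 12 months, SAP Tables 12–16 discard valid MMAS-4, CAT, mMRC, B-IPQ and awareness data whenever TSQM-9 is missing at the same visit

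*SAP*

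**What the plan says.** SAP 4.5 sets the denominator for the adherence table (Table 13): "Descriptives will be calculated over the number of patients respectively evaluable at the time point considered". It then spells out that this means the FAS at enrolment and the evaluable sets at 6 and 12 months. SAP 4.4, 4.6 and 4.8 (Tables 12, 14 and 16) carry the same rule, and SAP 4.7 (Table 15) uses those sets for its percentages.

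The follow-up sets are defined by satisfaction data. Besides FAS membership and a visit within the window, criterion 13 asks for "patients with at least one Treatment Satisfaction Questionnaire for Medication (TSQM-9) domain score calculated at 6-month follow-up visit", and criterion 16 asks for "patients with at least one Treatment Satisfaction Questionnaire for Medication (TSQM-9) domain score calculated at 12-month follow-up visit". SAP section 3 adds for TSQM-9: "Each domain score can be calculated only if all the three items considered in the calculation of that score are not missing".

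A footnote to Chart 1 (SAP 2.3) covers the patient-reported outcome rows: "Patients having PRO score computable at the visit will be considered for this analysis".

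MMAS-4 has its own rule in SAP section 3, with no reference to TSQM-9: "The score can be calculated if at least 3 out of 4 of the items are completed". The scale runs from 0 to 4, and "a higher score means better adherence to therapy".

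Protocol 9.1 says: "The patients switching or stopping treatment during observation period will not be withdrawn from the study".

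**The concern.** For Tables 10 and 11 the TSQM-9 condition costs nothing, because without a TSQM-9 score there is nothing to summarise. For Tables 12–16 it removes usable data. A patient who attends month 6 or 12 and completes MMAS-4, CAT, mMRC, B-IPQ and the awareness interview, but completes no TSQM-9 domain, disappears from all five tables at that visit.

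Four of those instruments are the whole of secondary objective #1. Conditioning them on a second questionnaire means the tables describe patients who also rated their medication that day, not everyone with a valid score. Adherence is the result most exposed. If patients who have disengaged from treatment are more likely to leave TSQM-9 blank, MMAS-4 is where that disengagement would show, and those are the scores removed.

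**Working it through.** **1. Follow one patient through the rules.** Take a FAS patient seen within the window at month 12, with four MMAS-4 items answered and no TSQM-9 domain complete.

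- MMAS-4 scoring (SAP section 3): computable.
- Criterion 16 (SAP 2.3): fails, so not evaluable at 12 months.
- Table 13 denominator (SAP 4.5): excluded.
- SAP section 4, general rule: patients with missing data are left out of analyses of the variable that is missing. MMAS-4 is not missing, so this rule would keep the patient.
- Protocol 9.7, analysis population: at least one TSQM-9 domain score, no visit named. The FAS already requires one at enrolment, so this condition is met.
- Protocol 9.7, missing values: such patients are not to be excluded.
- Protocol 9.7, stopping treatment: censoring is stated for the primary objective and objectives #2 and #4. None is stated for objective #1.

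Only criteria 13 and 16 remove the patient. SAP 4.9 declares and dates its departure from the protocol on model covariates; no similar statement is made here.

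**2. Reproduce the plan's own figures.** Protocol 9.5 has no figure for MMAS-4. Its sample sizes and TSQM-9 precision reproduce:

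- N = 400 × (1 − 0.05) = 380 and 400 × (1 − 0.20) = 320.
- Half-width = 1.96 × SD / √N. For SD 21.4 and N = 320: 1.96 × 21.4 / √320 = 2.345, as printed. The other three entries (2.152, 1.669, 1.819) also agree.

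**3. Possible shift in the MMAS-4 mean.** Let f be the share of MMAS-4 completers at a visit with no complete TSQM-9 domain, m1 the mean MMAS-4 of those kept, and m0 the mean of those dropped.

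Reported mean − mean over all completers = m1 − [(1 − f)m1 + f·m0] = f × (m1 − m0).

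The documents give neither f nor m1 − m0, so every value below is an assumption.

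| f (assumed) | Dropped if 320 completers | Gap 0.5 | Gap 1 | Gap 2 |
|---|---|---|---|---|
| 1% | 3 | 0.005 | 0.01 | 0.02 |
| 2% | 6 | 0.01 | 0.02 | 0.04 |
| 5% | 16 | 0.025 | 0.05 | 0.10 |
| 10% | 32 | 0.05 | 0.10 | 0.20 |
| 20% (extreme) | 64 | 0.10 | 0.20 | 0.40 |

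If m1 = m0 the shift is 0. If m1 < m0 it reverses sign.

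**4. Scale.** With an assumed SD of 1.2 and n = 320, the 95% half-width is 1.96 × 1.2 / √320 = 0.13. For SDs of 1.0 to 1.5 and n of 320 to 380 it is 0.10 to 0.16. A shift of 0.13 needs f = 0.13 / 1 = 13% at a 1-point gap, or 0.13 / 2 = 6.5% at a 2-point gap.

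Table 13 also reports Yes/No items. With an assumed 25-percentage-point gap, f of 2% to 10% shifts a proportion by 0.5 to 2.5 percentage points. The half-width at a proportion of 50% and n = 320 is 1.96 × √(0.25/320) = 5.5 percentage points.

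**The case against.** **The TSQM-9 condition comes from the protocol.** True in part. Protocol 9.7 restricts the analysis to patients with at least one TSQM-9 domain score and makes no exception for objective #1. But it names no visit, and the FAS already meets it at enrolment. The per-visit requirement is the SAP's addition.

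**A common set per visit lets satisfaction and the other scores be read on the same patients.** This is a reasonable aim, but the SAP does not state it, and it does not need valid data to be removed from the main descriptive tables.

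**The Chart 1 footnote may already allow what is asked.** It is attached to marks inside the evaluable-set columns, so the likelier reading is that it narrows those sets. If it was meant to replace them, it conflicts with SAP 4.4–4.8, which name the evaluable sets outright. Either way the text needs correcting, because two programmers could produce different denominators.

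**The effect on adherence is speculative.** This stands. A reader might infer that the dropped patients are those with no drug to rate, and that follow-up adherence is therefore biased upward. The documents do not support that:

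- The TSQM-9 instruction (SAP Appendix 8.3) lets patients answer by reference to their last use, so someone who stopped can still respond.
- One complete domain of three keeps a patient in.
- Protocol 9.7 expects few patients to stop.
- MMAS-4 (SAP Appendix 8.6) also asks about the patient's own medicine, so a patient with no current drug may not complete it either.

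**The 5–20% drop-out range does not measure the number dropped.** Also right. Protocol 9.5 pools not evaluable, lost to follow-up and off-treatment patients. Those lost have no MMAS-4 to discard.

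**Other provisions give visibility.** Table 2 lists reasons for non-eligibility. SAP 4.2 allows an optional selection-bias check on baseline characteristics. Protocol 9.13 promises a description of patients with and without TSQM-9 scores. None of these returns the discarded follow-up scores to Tables 12–16.

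**Conclusion.** The point holds as a matter of analysis sets. As written, Tables 12–16 at 6 and 12 months discard valid scores on five instruments when TSQM-9 is missing at that visit. This goes beyond the protocol's evaluability rule and fits poorly with the SAP's own missing-data rule. That conclusion rests on the text and on no assumed number.

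The consequence is not established. The number affected is unknown and may be small. Follow-up adherence could be overstated if those dropped are mainly poor adherers, but neither direction nor size can be shown. With 2–10% dropped and a 1–2 point gap, the MMAS-4 mean shifts by 0.02 × 1 = 0.02 to 0.10 × 2 = 0.20 points, against a half-width of about 0.13 (SD 1.2, n = 320, all assumed). That ranges from negligible to larger than the reported uncertainty.

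Two further inferences should be resisted. Changes from enrolment are within-patient differences, and the calculation above concerns follow-up levels only, so nothing shows that changes would look better than they are. For CAT, mMRC, B-IPQ and awareness there is a loss of data but no basis for a direction.

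The primary objective is unaffected. The change is worth making because it recovers valid data at almost no cost.

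**What to change.** - For Tables 12–16 at 6 and 12 months, use all FAS patients with that instrument computable at that visit, without criteria 13 and 16.
- Reword the denominator sentences in SAP 4.4–4.8 and the Chart 1 footnote so that both say this.
- Keep criteria 13 and 16 for the TSQM-9 tables.
- Print n for each instrument and visit. The table layouts in SAP section 5 are not visible in the public copy, so this may already be planned.

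The visit windows and the enrolment TSQM-9 requirement are separate matters and are not changed by this.

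The cost is a few sentences of SAP text and one changed filter. No new data are needed. Denominators will differ between instruments, which the printed n makes plain.
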